APPENDIX II**SCHEME FOR UNASSISTED VENTILATION WITH TRACHEOSTOMY**

The following suggested scheme can be used for unassisted ventilation with a tracheostomy, but should be individualized in every patient:

1. Unassisted ventilation for 30 minutes, three times per day
2. Unassisted ventilation for 1 hour, three times per day
3. Unassisted ventilation for 2 hours, three times per day
4. Unassisted ventilation for 4 hours, three times per day
5. Unassisted ventilation for 6 hours, two times per day
6. Unassisted ventilation for 18 hours
7. Unassisted ventilation for 24 hours

APPENDIX III

PATIENTS EXAMPLES FOR CLARIFICATION VENTILATION WITH 'RESTRICTED PEEP'-ARM

Patient A is intubated and ventilated due to decreased level of consciousness as a result of intoxication with presumed GHB. Patient A fulfills the inclusion criteria and is included in the RELAX study and randomized to the 'restricted PEEP'-arm. The ventilation is started with a PEEP level of 5 cm H₂O and FiO₂ of 0.4, the saturation is stable and remains SpO₂ > 94%. Following the flowchart, the oxygenation target range is reached and stable, hence the PEEP level can be 'down-titrated' with increments of 1 cm H₂O with reassessment of the saturation every 15 minutes following each adjustment of the PEEP level. The PEEP level is successfully 'down-titrated' to a PEEP level of 0 cm H₂O with a SpO₂ 93%. Since the oxygenation target range is reached and stable, the attending physician is able to decrease the FiO₂ level from 0.4 to 0.21.

Patient B is a trauma patient with a flail chest, and is intubated and ventilated due to respiratory insufficiency. Patient B is a candidate for the RELAX study and is randomized to the 'restricted PEEP'-arm. Ventilation is started with a PEEP level of 5 cm H₂O, soon the oxygenation target range is reached and the PEEP level is successfully 'down-titrated' to 0 cm H₂O with a FiO₂ of 0.3 while maintaining the oxygenation target (SpO₂ > 92%). The admission is complicated by a ventilator acquired pneumonia (VAP) and purulent secretion is noticed, treatment with antibiotics is started. On the fifth day of admission, suddenly the saturation drops to SpO₂ 88%. The FiO₂ is increased to 0.6 and the PEEP level was set back at 5 cm H₂O. Since lots of purulent secretion was removed earlier that day, a mucus plug is considered and the attending physician performs a recruitment maneuver successfully with improvement of oxygenation (SpO₂ 93%). During reassessment, the saturation remains stable and within the oxygenation target range, therefore the PEEP level can be 'down-titrated' again.

Patient C is admitted due to a respiratory infection. Patient C is intubated due to respiratory insufficiency which developed the same day and is admitted to the ICU. Patient C is eligible for the RELAX study and is randomized to the 'restricted PEEP'-arm. Ventilation is started with a PEEP level of 5 cm H₂O and a FiO₂ of 0.5, the saturation is SpO₂ 92%. Attempts for 'down-titration' of the PEEP level are unsuccessful and therefore the PEEP level and the FiO₂ remains unchanged. However, that afternoon the SpO₂ drops to 88%, the FiO₂ is increased to 0.6 and the PEEP level of 5 cm H₂O is maintained. During reassessment, the oxygenation target range is not reached and consequently adjustments are made with increasing the FiO₂ and the PEEP level further, until 10 cm H₂O and 0.8.

A chest radiograph is obtained with the appearance of bilateral infiltrates. Patient C is clinically diagnosed with ARDS, since the respiratory failure cannot be explained by cardiac failure or fluid overload. Ventilation is continued according to the existing ARDS guidelines.

APPENDIX IV

Substudy – ‘RELAXECHO’

Background

Cardiac function, in particular of the right ventricle, depends on intrathoracic pressures[1,2]. Use of positive end-expiratory pressure (PEEP) could increase right atrial pressure, pulmonary vascular resistances and right ventricular afterload[3-5]. The net effect of PEEP may be a decrease in right ventricle (RV) volume and output, with no changes in ejection fraction [3]. One small study showed a negative effect of high PEEP on right ventricular strain[6], a surrogate measure of contractility. It is uncertain whether low PEEP has an independent effect on right ventricle myocardial strain. The myocardial performance index (MPI) is regarded as an easy and reproducible echocardiographic parameter of both systolic and diastolic function. The MPI is relatively independent of changes in loading conditions in various clinical settings [8-11]. The RELAX study provides a unique opportunity to study cardiac performance and especially the performance of the right ventricle during varying levels of PEEP (between 0 and 8 cm H₂O) in patients with uninjured lungs.

Aim

The aim of RELAXECHO, a substudy of the RELAX study, is to assess and compare changes in cardiac function as measured by transthoracic echocardiography (TTE) in the two study groups.

Hypothesis

We hypothesize that ventilation with liberal PEEP decreases right ventricular function after 24-48 hours of mechanical ventilation.

Endpoint

The primary endpoint of this sub study is the myocardial performance index of the right ventricle in the first 24-48 hours of mechanical ventilation.

In- and exclusion criteria

Inclusion criteria:

- Admitted to the ICU of the Academic Medical Center
- Enrolled in the RELAX study

Exclusion criteria:

- Ventilation with PEEP > 2 cm H₂O in the 'restricted PEEP'-arm and ventilation with PEEP < 7 cm H₂O in the 'liberal PEEP'-arm
- Refractory circulatory instability requiring > 5 µg/kg/min dopamine or dobutamine, > 1 mg/hour milrinone, or norepinephrine dose of > 0.4 µg/kg/min
- Documented poor left ventricular function (e.g. left ventricular ejection fraction ≤ 30%)

Original sample size calculation

We estimated 28 patients in each study group to achieve a power of 80%, with a two-sided significance level of 0.05, to detect a 0.06 difference in change in myocardial performance index between ventilation with restricted PEEP (defined as a PEEP ≤ 2 cm H₂O) and ventilation with liberal PEEP (defined as a PEEP ≥ 7 cm H₂O), assuming a standard deviation of 0.08. The sample size is increased by 20% to correct for dropouts (i.e., if myocardial performance index cannot be determined from the TTE due to poor echogenicity), meaning that a total of 68 patients are required. The decision about the sample size is based upon the consideration that the quantity of PEEP has an effect on right ventricular function [6]. Differences in right ventricular function are expressed in the myocardial performance index, which is a parameter known to be relatively load-independent.

Sample size re-calculation

Based on the results of a recent study in a similar patient cohort, showing a much larger decrease of 0.23 in myocardial performance index with lower tidal volume reduction, [7] the sample size was recalculated on 12 November 2019 as follows. With a still conservative effect size on MPI of the right ventricle of 0.12 (an effect size half the size of the previous study [7]), and a mean MPI of the right ventricle of 0.41 and a standard deviation of 0.13, we need 18 patients in each study group to detect a difference of 0.12 in MPI of the right ventricle with PEEP reduction with 80% power with a two-sided significance level of 0.05. The sample size is increased by 20% to correct for dropouts, meaning that a total of 44 patients (22 per group) are required.

Methods

Cardiac ultrasound is performed within 24 to 48 hours after enrollment in the RELAX study. The cardiac echocardiography will be performed by trained physicians under supervision of cardio-intensivists, will perform the echocardiography, using the GE Healthcare Vivid 9 ultrasound machine with a 2–5 MHz sector probe. Traditional

echocardiographic measures, tissue Doppler imaging (TDI) and speckle tracking echocardiography (STE) parameters will be collected online and with post-acquisition offline analysis[12]. Images of the ventricles are analyzed offline for the myocardial performance index, strain and strain rate and diastolic parameters. Ultrasound clips will be saved for further offline STE analysis and quality control. Measurements will be performed after at least 5 minutes of stable mean arterial pressure. Bidimensional and Doppler measurements will be made in accordance with current recommendations of the American Society of Echocardiography[13].

Statistical analysis

Normally distributed variables are expressed by their mean and standard deviation; non-normally distributed variables are expressed by their medians and interquartile ranges. Categorical variables will be expressed as n (%). To test groups of continuous normally distributed variables, Student's t-test will be used. Likewise if continuous data is not normally distributed the Mann-Whitney U test will be used. Categorical variables will be compared with the Chi-square test or Fisher's exact tests or when appropriate as relative risks. Statistical significance is considered to be at a p-value of 0.05. Where appropriate, statistical uncertainty will be expressed by 95% confidence levels. Analysis will be performed with R (www.r-project.org).

Informed consent

Deferred informed consent from a legal representative is obtained as soon as possibly for this sub study as part of the parent study RELAX. In case a patient is awake and adequate informed consent will be obtained from the patient.

References

3. Pinsky MR. My paper 20 years later: Effect of positive end-expiratory pressure on right ventricular function in humans. *Intensive Care Med*. Springer Berlin Heidelberg; 2014;40:935-41.

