7.1.3 Other study parameters

Health care related costs will be estimated from the health systems perspective over the time horizon of this trial. Costs include costs of ventilation, costs of stay in ICU,

costs of stay in hospital, costs of use of inotropes and vasopressors, costs of use of sedatives, costs of use of tracheostomies, costs of ventilator-associated pneumonia. Costs will be determined for both PEEP arms during the 28 days follow up period after initial ICU admission. These are used to calculate incremental cost per mechanical ventilation-day avoided.

Lung ultrasound (LUS): within 12 hours after enrolment in the RELAX study, after 24-48 hours after enrolment and within 24 hours after extubation, a LUS will be performed to monitor changes in lung aeration. This is only done in patients admitted to the AMC (see appendix IV: RELAXLUS).

Cardiac ultrasound (ECHO): 24-48 hours after enrolment in the RELAX study, a transthoracic echocardiography (TTE) will be performed to assess the cardiac function. This is only done in a total of 68 patients admitted to the AMC (see appendix V: RELAXECHO).

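### Section 7.1.3 still gives 68 patients for the RELAXECHO substudy where Appendix IV now requires 44, and the 18 evaluable per group behind the 44 fall slightly short of the stated 80% power

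*Protocol*

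**What the plan says.** Section 7.1.3 (Other study parameters) describes the transthoracic echocardiography at 24 to 48 hours and limits it: "This is only done in a total of 68 patients admitted to the AMC". It refers the reader to an appendix for RELAXECHO.

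Appendix IV (RELAXECHO) holds two calculations.

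- The one headed as original assumes a difference of 0.06 and SD 0.08, gives 28 per group, and arrives at 68 in total after a 20% increase.
- The re-calculation, dated 12 November 2019, supersedes it. It starts "With a still conservative effect size on MPI of the right ventricle of 0.12", takes "a mean MPI of the right ventricle of 0.41 and a standard deviation of 0.13", and asks for "80% power with a two-sided significance level of 0.05". It concludes "we need 18 patients in each study group to detect a difference of 0.12" and then "The sample size is increased by 20% to correct for dropouts, meaning that a total of 44 patients (22 per group) are required".

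The statistical analysis paragraph of the same appendix names Student's t-test for normally distributed continuous variables and the Mann-Whitney U test otherwise.

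**The concern.** There are two separate problems.

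First, the size in section 7.1.3 is the superseded one. That section is operative protocol text, not a log of changes, and nothing there marks 68 as out of date. Someone working from the main body and someone working from the appendix would hold different targets.

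Second, the re-calculated 18 per group is presented as sufficient for 80% power. If the appendix's own inputs do not give that, the power statement is wrong as written. A reader interpreting a null substudy result would then credit it with slightly more sensitivity than it has.

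**Working it through.** **Enrolment totals, side by side**

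| Place | Total | Status in the text |
|---|---|---|
| Section 7.1.3 | 68 | current, unqualified |
| Appendix IV, original calculation | 68 | labelled as original |
| Appendix IV, re-calculation | 44 | dated replacement |

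The gap is 68 − 44 = 24 patients.

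**Inputs for the power check** (Appendix IV, re-calculation): difference Δ = 0.12, SD σ = 0.13, two-sided α = 0.05, power 80%, two equal groups. Standardised difference d = 0.12 / 0.13 = 0.923.

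**Reproducing the plan's figures, normal approximation**

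n per group = 2 × [(z₀.₉₇₅ + z₀.₈₀) × σ/Δ]²

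- Original calculation: 2 × [(1.960 + 0.842) × 0.08/0.06]² = 27.9, so 28, as stated. A noncentral t calculation gives 28.9, so 29.
- Re-calculation: 2 × [(1.960 + 0.842) × 0.13/0.12]² = 18.42. Rounded up this is 19; the plan has 18.

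The normal approximation fits both stated figures best. In the second case the result appears to have been rounded down.

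**Power at 18 per group**

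- Normal approximation: Φ(d × √(n/2) − 1.960) = Φ(0.923 × 3 − 1.960) = Φ(0.809) = 79.1%.
- Two-sample t-test (noncentral t, 34 degrees of freedom): 76.7%.

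**Size needed for 80%**

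- Normal approximation: 18.42, so 19 per group (81.2%).
- t-test: 19.43, so 20 per group (81.2%); 19 per group give 79.1%.

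**Difference detectable with 80% power at 18 per group, t-test:** the required d is 0.961, and 0.961 × 0.13 = 0.125.

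**Dropout step**

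- As the plan does it: 18 × 1.2 = 21.6, so 22 per group and 44 in total. This reproduces the stated total.
- If 18 of 22 remain evaluable, the loss covered is 4/22 = 18.2%.
- If a full 20% of the 44 were lost: 22 × 0.8 = 17.6 per group. Power is then 75.8% by t-test and 78.2% by the normal approximation.

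**Evaluable patients per group and power**

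| Evaluable per group | t-test | Normal approximation |
|---|---|---|
| 17.6 | 75.8% | 78.2% |
| 18 | 76.7% | 79.1% |
| 19 | 79.1% | 81.2% |
| 20 | 81.2% | 83.1% |
| 22 (no loss) | 84.9% | 86.5% |

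**The case against.** Appendix IV does not name its formula. On the normal approximation, which also reproduces the original 28, power at 18 is 79.1% and the only slip is rounding 18.42 down. That is fair, and it limits the size of the point. It does not remove it, because 18 misses 80% by this method too, and the planned test is a t-test, for which the miss is about three points.

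The practical effect is also small. A move from 0.12 to 0.125 in the detectable difference lies well within the uncertainty of an assumed SD and a deliberately reduced effect. With at most two patients lost per group, 44 would still give at least 80%. This stands.

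On the totals, a reader who turns to Appendix IV can see which figure is current. That makes the contradiction easy to resolve, but section 7.1.3 still states the wrong number.

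A reader might infer three stronger points, which the protocol does not support:

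- *That the plan's own figures give about 76% power.* This needs both the t-test calculation and a 20% loss. The appendix describes a 20% increase to allow for dropouts, and 22 enrolled with 18 remaining is consistent with that. About 76% is a scenario, not the plan's stated case.
- *That 0.12 misrepresents the earlier result.* The appendix calls it "an effect size half the size of the previous study", whose decrease was 0.23. Half of that is 0.115, which is 0.12 to two decimals, the precision used throughout that paragraph. This is rounding.
- *That two totals in an open trial leave room to choose when to stop the substudy.* Appendix IV dates its replacement figure, and the protocol describes no interim look at the echocardiography data. This would be conjecture.

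**Conclusion.** The contradiction between 68 in section 7.1.3 and 44 in Appendix IV is firm and rests on no assumption: a superseded figure was left in current text.

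The stated power is also wrong as written, by a small amount. With Δ = 0.12, SD 0.13 and two-sided 0.05, 18 evaluable patients per group give about 77% with the planned t-test and 79% by the normal approximation, against the stated 80%. The sizes that reach 80% are 20 and 19 evaluable per group respectively. The t-test figures assume normal data with a common SD of 0.13. If a full 20% of the 44 were lost, t-test power would be about 76%.

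Both matters are confined to the substudy and leave the trial's primary endpoint and sample size untouched. The first is the reason to amend; the second can be corrected in the same edit.

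**What to change.** 1. In section 7.1.3, replace 68 with the current Appendix IV target of 44. The same section cites RELAXECHO as appendix V and RELAXLUS as appendix IV, whereas the appendices carry the opposite numbers; correct these references too.
2. In the Appendix IV re-calculation, restate what the chosen size delivers, for example: *44 enrolled, with 18 evaluable per group, give about 77% power for a difference of 0.12 by two-sided t-test (SD 0.13), or 80% power for a difference of about 0.125; if 20% of the 44 are lost, power for 0.12 is about 76%.*

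The cost is a few words in two places and a slightly less favourable power statement. No additional patients are required.

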APPENDIX V

Substudy – ‘RELAXLUS’

Background

Ventilation with low PEEP may increase the risk of atelectasis in critically ill patients receiving invasive ventilation, as has been shown before in patients undergoing intraoperative ventilation (1, 2). Lung ultrasound (LUS) is a non-invasive relatively simple bedside technique used to semi-quantify changes in lung aeration in ventilated patients (3), and very capable to detect atelectasis (4).

Aim

The aim of RELAXLUS, a substudy of the RELAX study, is to assess and compare changes in pulmonary aeration and presence of atelectases as detected by LUS in the two study groups.

Hypothesis

We hypothesize that ventilation with restricted PEEP results in a decrease in lung aeration and an increase in atelectases.

Endpoint

The primary endpoint of this sub study is the change in lung ultrasound aeration score in the first 48 hours of invasive ventilation.

In- and exclusion criteria

Inclusion criteria:

- Admitted to the ICU of the Academic Medical Center
- Enrolled in the RELAX study

Exclusion criteria:

- Evidence of cardiac failure or fluid overload, based on an objective assessment such as echocardiography in the medical record and/or on judgment of the treating physician

Methods

LUS is performed at three predefined time points: within 12 hours after enrolment in the RELAX study (this LUS examination is standard of care in patients that are expected to need invasive ventilation > 24 hours), between 24 to 48 hours after enrolment and within the first 24 hours after extubation. Experienced and trained physician will perform LUS examinations, using a 2–5 MHz convex probe. Each

hemithorax is divided into six areas: the anterior, lateral and posterior areas, each divided in upper and lower quadrants, using the parasternal line, the anterior axillary line, the posterior axillary line and the paravertebral line as borders (Figure 1). The 12 regions are examined and a semi-quantitative score is calculated to estimate lung aeration at each time point, and documented in a case report form (see Table 1). Additional sonographic signs previously described for atelectasis will be reported when present for each of the 12 lung regions examined. These include the absence or reduction in lung sliding, the presence of subpleural consolidations and presence of static air bronchograms in consolidated areas (5).

[figure not shown]

Figure 1. Six zones are scanned per hemithorax.

Table 1. LUS aeration score

Pattern	Score	View	Interpretation
A	0	Only A lines visible or isolated ≤ 2 B-lines	Normal lung aeration
B1	1	Multiple well-defined either regularly spaced or irregularly spaced B-lines	Moderate loss of lung aeration
B2	2	Multiple coalescent B-lines	Severe loss of lung aeration
C	3	Hypoechoic or tissue-like area	Consolidated lung tissue

Informed consent

Written informed consent is obtained for the two extra LUS examinations as part of the informed consent for the parent study (RELAX), i.e., the one between 24 and 48 hours after enrolment, and the one within the first 24 hours after extubation, as the first LUS examination is standard of care in these patients.

References

1. Martin JB, Garbee D, Bonanno L: Effectiveness of positive end-expiratory pressure, decreased fraction of inspired oxygen and vital capacity recruitment maneuver in the prevention of pulmonary atelectasis in patients undergoing general anesthesia: a systematic review. *JBI Database Syst Rev Implement*

Reports 2015; 13:211

APPENDIX VI

Substudy – ‘RELAXBiomarkers’

Background

Mechanical ventilation has a strong potential to inflame and damage lung tissue. Plasma level of several markers of inflammation and lung damage, including tumor necrosis factor (TNF)-alpha, Interleukin (IL)-6 and IL-8, the soluble form of the Receptor for Advanced Glycation End-products (sRAGE), Surfactant Protein (SP)-D, Clara Cell protein (CC)-16 and Krebs von den Lungen 6 (KL6), have been shown to rise in response to intraoperative ventilation and depending on ventilator settings used [1]2. Plasma levels of these biomarkers also rise in response to mechanical ventilation using large tidal volumes [2]. The RELAX trial offers the unique opportunity to study the dependence of plasma levels of biomarkers of inflammation and lung damage on the level of PEEP used during the first week of mechanical ventilation in patients with uninjured lungs.

Aim

The aim of RELAXBiomarkers, a substudy of RELAX, is to describe and compare changes in plasma levels of biomarkers of inflammation and pulmonary injury.

Hypothesis

We hypothesize that ventilation with liberal PEEP, compared to ventilation with restricted PEEP, increases plasma levels of biomarkers of inflammation and pulmonary injury.

Endpoints

The endpoint of this substudy is the difference in plasma levels of biomarkers of inflammation and pulmonary injury between the two study groups.

In- and exclusion criteria

Inclusion criteria

- Admitted to the ICU of the Academic Medical Center
- Enrolled in the RELAX study

Exclusion criteria

- Receiving immunosuppressive medication

Methods

Blood sampling and handling

Left-over blood from arterial blood samples used for arterial blood gas analysis, taken as part of standard of care in the morning, will be collected within 12 to 16 hours after enrolment in the RELAX study, and thereafter till day 7 or until ICU discharge, whichever comes first.

Blood samples are centrifuged at 2,000 rpm for 15 minutes. Supernatant is collected and stored at -80°C until batchwise analysis, using customized Luminex kits for measurements of biomarkers of inflammation and lung injury, including TNF-alpha, IL-6, IL-8, sRAGE, SP-D, CC-16, and KL6.

Statistical analysis

Variables are expressed in mean plus standard deviation, or medians plus interquartile ranges where appropriate. Categorical variables are expressed as proportions. Student's t and Mann-Whitney U test are used depending on distribution of data. Categorical variables will be compared with the Chi-square test or Fisher's exact tests or when appropriate as relative risks. Statistical significance is considered to be at a p-value of 0.05. Where appropriate, statistical uncertainty will be expressed by 95% confidence levels. All analysis will be performed with R (www.r-project.org).

Informed consent

Written informed consent for the use left-over blood from arterial blood samples is asked as part of the informed consent for the parent study, RELAX.

References

1. Serpa Neto A, Campos PPZA, Hemmes SNT, Bos LD, Bluth T, Ferner M, et al. Kinetics of plasma biomarkers of inflammation and lung injury in surgical patients with or without postoperative pulmonary complications. *Eur J Anaesthesiol*. 2017;34:229–38.

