7.3 Study procedures

Patients in participating intensive care units (ICU) are screened and randomized within 1 hour after start of mechanical ventilation. Demographic data of all screened patients, regardless of meeting the enrollment criteria will be recorded (age, gender, expected duration of ventilation > or < than 24 hours).

The oxygenation target ranges for SpO₂ and PaO₂ are 92% to 96%, and 8 kPa to 11.5 kPa, respectively.³⁹⁻⁴³ Oxygenation will be maintained in the target ranges primarily by adjusting the FiO₂, which is typically set between 0.21 and 0.6. The oxygenation target is primarily assessed by SpO₂, as measured by pulse oximetry and only in case of discrepancy unreliable reading the oxygenation will be assessed by the PaO₂. Therefore, no extra arterial blood gasses need to be obtained, besides the normally, 3-4 daily conducted arterial blood samples.

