For these reasons, we opt for using deferred consent, where informed consent from a legal representative must be obtained as soon as possible, but always within 48 hours after randomization. If informed consent is not obtained, or if a legal representative denies participation within the time window of 48 hours, the patient is excluded and data will no longer be used. Thenceforth the patient is ventilated according to the policy of the attending physician.

Textbox 3 - Ventilation has the potential to harm the lungs – even after a short period of ventilation

Ventilation can harm the lungs, even after a short period of ventilation. If a patient, in the proposed trial, is already ventilated for several hours, injurious effects of ventilation could already be in place, largely reducing validity of the trial outcomes. From experimental animal studies we know that mechanical ventilation can cause effects within hours of ventilation with a high PEEP level.⁵⁷ These findings are in line with results from clinical studies, showing ventilator-related effects after relative short periods of ventilation, e.g. after ventilation during general anesthesia for surgery.⁵⁸ A recent randomized controlled trial of patients undergoing cardiac surgery with hypoxemia, comparing a ventilation strategy including a PEEP level of 8 cm H₂O with a ventilation strategy with a PEEP level of 13 cm H₂O, showed an important effect of mechanical ventilation on the incidence of postoperative pulmonary complications.⁵⁹

Textbox 4 – Experiences with deferred consent in critically ill patients

Most critically ill patients who need ventilation cannot be approached for informed consent for a study at ICU admission. Indeed, those patients are usually in severe respiratory distress, sedated or in coma. A prospective observational study on study recruitment practices in critically ill patients performed by a respected and experienced research group in Canada showed that the time from recognizing study eligibility to obtaining informed consent by a legal representative was as high as 12 hours, even while time from recognition to the first contact with a legal representative was as short as 2 hours.⁵⁵

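### RELAXBiomarkers: the first sample must be a routine morning draw and also fall 12 to 16 hours after enrolment, which most patients probably cannot meet, and no earlier value is kept as a reference for change

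*Protocol*

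**What the plan says.** Appendix VI (RELAXBiomarkers, Methods) uses what remains of routine arterial gases, "taken as part of standard of care in the morning, will be collected within 12 to 16 hours after enrolment". Sampling then goes on to day 7, or to ICU discharge if that is earlier. No sample before 12 hours is described.

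The aim and the endpoint are worded differently. The aim is to "describe and compare changes in plasma levels of biomarkers of inflammation and pulmonary injury". The endpoint reads: "The endpoint of this substudy is the difference in plasma levels of biomarkers of inflammation and pulmonary injury between the two study groups".

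Four other places bear on the point:

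- Section 4.1 has consecutive patients randomized within an hour of starting invasive ventilation, or on ICU admission if they arrive ventilated. Enrolment is not tied to the clock.
- Section 7.3 says no extra arterial gases are needed "besides the normally, 3-4 daily conducted arterial blood samples".
- Section 5.2 lowers PEEP in the restricted arm from 5 cm H₂O in 1 cm H₂O steps every 15 minutes, as far as 0 if oxygenation allows.
- Textbox 3 in section 10.2.1 cites animal studies in which mechanical ventilation "can cause effects within hours of ventilation with a high PEEP level".

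**The concern.** A morning draw is fixed to the clock. A window of 12 to 16 hours is fixed to enrolment. When enrolment can happen at any hour, the two coincide only for patients enrolled in a particular part of the day. With a 06:00 draw, a patient enrolled at 08:00 reaches the next morning draw at 22 hours and one enrolled at 22:00 reaches it at 8 hours; neither is in the window.

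Staff then have two options. If they follow the text, the first time point is missing for many patients. If they take the next morning draw anyway, first samples are spread over 0 to 24 hours of exposure and the time point loses its meaning.

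The second problem is the reference value. The protocol itself argues that ventilation acts within hours and lets the arms separate quickly. A first sample at 12 hours or later may already contain part of the response, so using it as the starting point for change could hide part of the effect. An analysis plan cannot repair this, because blood that was not stored cannot be measured later.

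**Working it through.** The substudy states no sample size, power or expected number of samples, so there is no figure of the plan's own to reproduce. The check is how often both conditions can be met.

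**Inputs from the protocol.** Window 12 to 16 hours after enrolment, 4 hours wide (Appendix VI). Routine morning draw (Appendix VI). 3-4 routine arterial samples a day (7.3). PEEP steps of 15 minutes (5.2).

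**Assumed.** Clock times of enrolment and of the draw, which the protocol does not give.

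**Is it a two-sided window?** Appendix IV (RELAXECHO, Methods) uses the same construction, within 24 to 48 hours after enrolment, and section 7.1.3 gives that examination as 24-48 hours. This supports a lower as well as an upper bound here.

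**Fixed draw, uniform enrolment.** A draw at hour T fits enrolments from T − 16 to T − 12. The share is 4/24 = 16.7%. A 06:00 draw fits enrolments from 14:00 to 18:00; an 08:00 draw fits 16:00 to 20:00.

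**Draw placed to suit the patient in a morning of w hours, uniform enrolment.** The eligible band widens to 4 + w hours:

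- w = 2: 6/24 = 25%
- w = 4: 8/24 = 33%
- w = 6: 10/24 = 42%

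This is generous, because it lets a routine draw move to fit each patient. If the draw merely varied within the morning independently of enrolment, the share would stay at 4/24.

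**Daytime-weighted enrolment.** Let a share s be enrolled evenly between 08:00 and 20:00 and the rest evenly overnight.

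- Fixed 06:00 draw: 4 × s/12, which is 17% at s = 0.5 and 30% at s = 0.9. Over fixed draws from 05:00 to 10:00 the range is 17-30%.
- Draw placed freely from 06:00 to 10:00 (enrolments 14:00 to 22:00): 6 × s/12 + 2 × (1 − s)/12, which is 33% at s = 0.5 and 47% at s = 0.9.

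**When would more than half qualify?** For a fixed draw, only if over half of patients were enrolled in one particular 4-hour slot. For a freely placed draw it takes a longer morning and strongly daytime enrolment together. For example, 05:00 to 11:00 (enrolments 13:00 to 23:00) with s = 0.9 gives 7 × 0.9/12 + 3 × 0.1/12 = 55%.

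**Any routine gas instead of the morning one.** With k equally spaced gases a day, the chance that one falls in a 4-hour window is 4/(24/k): 50% for k = 3 and 67% for k = 4.

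**Early values.** Under the stated window, no patient has a planned sample before 12 hours. The restricted arm can go from 5 to 0 cm H₂O in 5 × 15 = 75 minutes at the fastest, so the first sample can come well after the arms have separated.

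**The case against.** The strongest reply is that the stated endpoint does not need a baseline. It is a difference in levels between arms, and randomization supports that comparison without one. This stands. An early value would add precision and serve the aim, but the endpoint can be estimated without it.

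A reader might infer that no change at all can be measured and that the substudy can only compare levels. The text does not support that: sampling continues to day 7 or ICU discharge, so change after the first sample can be described and compared. What is missing is change from a value before or soon after the strategy begins.

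A reader might also infer that selection by hour of enrolment, or first samples spread over the day, biases the arm comparison. Hour of enrolment is fixed before randomization and has the same expected distribution in both arms. Irregular timing adds variance and blurs the time point; it does not confound the arms. Nor does missing the first window remove a patient, since later samples remain usable and the first is not made a condition for analysis.

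Finally, the phrase might mean only no later than 16 hours. Then 16/24 = 67% would have a qualifying morning draw and some would have an early value. The RELAXECHO usage makes this the weaker reading. Even so, first samples would range from 0 to 16 hours of exposure.

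**Conclusion.** The point holds in a limited form. As written, the first sample is missing or outside its window for most patients: about 17% can meet both conditions with a fixed draw and uniform enrolment, and roughly 17-47% across the main patterns examined. These shares rest on assumed clock times and on reading the window as two-sided. A long morning with a freely moved draw and heavily daytime enrolment could take the share just past half.

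The consequence is fewer observations and less precision at one time point. Separately, there is no early reference for an aim framed as change, and the aim and endpoint do not match. This is a minor matter in a single-centre substudy on left-over blood and touches nothing in the main trial.

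**What to change.** In Appendix VI:

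1. Drop the morning condition for the first sample and use whichever routine arterial gas falls 12 to 16 hours after enrolment. This improves coverage but does not complete it. If processing outside morning hours is not feasible, replace the window with the first morning draw after enrolment.
2. Store left-over blood from the first routine gas after enrolment as an early reference. With 3-4 equally spaced gases a day, it arrives within 24/3 = 8 or 24/4 = 6 hours.
3. Record hours from randomization for every sample, and adjust the arm comparison for the early value and for sampling time. Because the early value is taken after randomization and may already carry some effect, report the comparison without that adjustment as well.
4. Align aim and endpoint: either name change from the early sample as an endpoint, or word the aim as a comparison of levels over the first week.

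The cost is a change to the appendix wording, one more stored aliquot per patient from blood already drawn, and some centrifugation and freezing outside morning hours. The last is the main practical burden, and the alternative in step 1 avoids it only for the 12-to-16-hour sample.
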